4.3.2 Maximum Dose/Exposure for This Study

As above, because of the inhaled route of delivery, estimated lung burden was used to determine the maximum allowable exposure based on the lung burden at the dog NOAEL dose. As demonstrated, the dog NOAEL dose corresponds to a delivered human dose of 500 µg. However, in general there were few preclinical findings in either rat or dog safety studies. The NOAEL dose in dogs was 0.02 mg/kg/day; at the three-fold higher dose of 0.06 mg/kg/day, only mild focal bronchial artery thickening was observed, that occurred in one animal in the study.

For the studies in healthy volunteers, the maximum human dose was 240 µg, which provided a ~2-fold safety margin below the NOAEL. In accordance with EMA guidance for first-in-human studies (*Guideline on Strategies to Identify and Mitigate Risks for First in Human and Early Clinical Trials with Investigational Medicinal Products*), this conservative safety margin was applied because the study involved healthy participants. At this dose level, the compound was well tolerated and all safety data was within normal parameters. In addition, the observed pharmacokinetic data established that systemic exposures to the compound were well below the systemic NOAEL level established in dogs.

Having established the tolerability of 240 µg in normal healthy participants, the present study will involve participants in the target population for this therapy. The maximum dose will be advanced to a maximum of 480 µg, which is below the NOAEL dose. The preclinical finding that was noted in dogs appears to be due to a vasoactive pharmacological effect within the

lung, presumably vasodilation induced by MK-5475. Since pulmonary hypertension patients suffer from chronic vasoconstriction, it is likely that they would be better able to tolerate acute vasodilation of blood vessels in the lung without harmful sequelae than healthy participants. In addition, we note that although 100% deposition in humans is assumed in these calculations, the true deposition based on the fine particle fraction is lower (~30-60%), affording an additional safety margin. Therefore, the true lung exposure will be lower than projected above. Thus, a less conservative safety margin is appropriate in patients than in healthy participants, as these participants may potentially benefit directly from development of an additional therapy for their disease.

Finally, although systemic exposure is considered less relevant for inhaled compounds, based on the observed PK data from the prior study, it was initially projected that systemic exposure will also be approximately 2-fold below the observed AUC 0-24h of 4.5 nM*hr from the dog NOAEL dose at the 240 µg dose. Based on the initial PK data observed in this study for participants in Panel A, the observed systemic PK at a dose of 240 µg was substantially lower than projected, with AUC 0-24h of 1.42 nM*hr. Given the low gastrointestinal bioavailability of this compound, and the observed direct proportionality between delivered dose and systemically measured PK, this reduced exposure was thought to be related to the decreased ability of diseased patients to generate adequate inhaled exposure compared with healthy subjects (as the lung deposition of inhaled DPI compounds is directly affected by the inspiratory flow generated by the subject). As the dose in this study was increased to 300 and then 360 µg, subsequent participants have exhibited higher exposures. In order to further explore the relationship between systemic exposure and delivered dose at higher doses, the maximum dose will be increased in this study to 480 µg. At this dose, the resulting systemic exposure is projected to be approximately 3.5nM*hr AUC 0-24h. While participants may exceed the NOAEL systemic exposure, this exposure was set on the basis of a local finding in the lung in a 30-day toxicology study. In contrast, the finding which was used to set the NOAEL is expected to be driven by lung burden, which at this dose remains below the NOAEL dose of 500 µg. While higher systemic exposures from a single dose may lead to hemodynamic changes, such changes were only observed in preclinical species at systemic exposures far above the NOAEL exposure in pharmacology studies. No evidence of any impact on systemic hemodynamics including heart rate or blood pressure has been observed thus far in any clinical study of MK-5475, and given the short systemic half-life of this compound, it is expected that any such change after a single dose of compound would be self-limited. Finally, a subsequent 3-month GLP toxicology study showed that the finding used to establish the NOAEL was no longer present in a longer duration study.

The estimated total radiation burden per participant after the completion of all CT scans will not exceed the maximum limit of 10 mSv [Directorate-General, Environment Nuclear Safety and Civil Protec 1998]. If there is a need for fluoroscopy during RHC, the total radiation exposure during RHC will be equivalent to the amount of radiation the participant would receive if fluoroscopy was performed during RHC for initial diagnosis or follow-up. This study does take into account the desired yearly limit for study participants as per ICRP publication 62.

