2.2.3 Ongoing Clinical Studies

PN002: Dosing of MK-5475 in Participants with Pulmonary Hypertension (Current Study)

In this 2-part study evaluating the safety, PK and PD [right heart catheterization (RHC) and functional respiratory imaging (FRI)], single-dose MK-5475 ranging from 120 to 360 µg in participants with moderate to severe group 1 PAH is generally well-tolerated. To date, no serious adverse events (SAEs) were reported and no participants discontinued due to an AE. Adverse events (AEs) were mild to moderate in intensity. A total of 45 AEs in 15 of 18 participants were reported. Of these, 9 AEs were considered related to study drug by the investigator. AEs deemed related were rhinitis (1), dizziness (1), ALT increased (2.94 x ULN) (1) bilirubin increased (1.18 and 2.13 x ULN)(2) hyperkalemia (1.02 to 1.07 xULN) (3) and platelet count decreased (0.33 below LLN) (1). Refer to the Investigator's Brochure for a full listing of AEs to date.

Following single inhaled MK-5475 administration, moderate to high inter- and intra-individual variability in AUC and C_{max} was observed in PAH participants compared to healthy participants. Geometric mean AUC₀₋₂₄ in PAH participants ranged from 0.259 to 4.28 nM*hr for the 120 to 360 µg dose levels across study panels/periods. Geometric mean AUC₀₋₂₄ in PAH participants at 240 µg ranged from 1.04 to 1.71 nM*hr. Geometric mean AUC₀₋₂₄ in PAH participants at the 300 µg dose level ranged from 2.08 to 2.35 nM*hr across study panels, The geometric mean AUC₀₋₂₄ at the 360 µg dose level in PAH participants ranged 1.21 to 4.28 nM*hr. Geometric mean AUC₀₋₂₄ in all study populations thus far has remained below the AUC₀₋₂₄ corresponding to NOAEL in 1 month tox study in dogs (4.5 nM*hr). A total of four PAH participants reached an AUC₀₋₂₄ higher than the dog NOAEL exposure in at least one of the periods in the study: one dosed at 300 µg (7.25 nM*hr) and three dosed at 360 µg (4.53 to 6.99 nM*hr). The highest individual AUC₀₋₂₄ at the 360 µg dose level in PAH participants was 6.99 nM*hr which is about 1.6-fold above the NOAEL. Although this was above the 1-month dog NOAEL, the total dose delivered remained below the NOAEL dose of 500 µg. Safety and tolerability profile in participants in whom individual AUC₀₋₂₄ levels exceeded the NOAEL AUC₀₋₂₄ appears similar to other participants.

PN004: MK5475 Sildenafil DDI Study

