4.2 Scientific Rationale for Study Design

This study is being conducted to evaluate safety, tolerability, pharmacokinetics, and pharmacodynamics of MK-5475 after administration of a single dose to participants with PAH. Preclinical studies as well as the first-in-human study with this compound support the conduct of this study, given the evidence that the compound appears to be safe, well-tolerated, and has suitable pharmacokinetics to support a pharmacodynamic evaluation.

Because this is the first introduction of this compound into participants with PAH, Part 1 of the study was designed to evaluate safety, tolerability, and pharmacokinetics in this population. As a conservative measure to ensure participant safety, dosing began at 120 µg, a level below the maximum dose of 165 µg that was given to healthy participants in PN001. The dose was gradually escalated first to 165 µg and then to the maximum dose of 240 µg in Part 1. In Part 2 Panels B and C, the dose will begin at 300 µg and escalate to 360 µg (See Section 4.3.2). Given the favorable safety profile observed in the preclinical 3-month toxicology studies and in clinical studies at doses up to 360 µg and to further explore the range of possible safe and effective doses of MK-5475, a dose of 480 µg of MK-5475 will be given in the first period of Panel D. In periods 2 and 3 of Panel D, a dose of 120 µg will be given in order to explore the PK/PD relationship at a lower dose.

Once the safety, tolerability, and pharmacokinetics have been established in Part 1 and Part 2, Period 1, pharmacodynamic assessments will be performed in a larger group of participants. These assessments (right heart catheterization and functional respiratory imaging) are directly related to the ultimately desired clinical efficacy endpoints for this compound and are well-validated in the published literature [Grimminger, F., et al 2009].

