Secondary (PK): Separately for each PK parameter (in Panel A, Part 1, Periods 1~3, and Panel B-D, Part 2, Period 1), individual values of AUC_{0-24hr} , $AUC_{0-\infty}$, C_{max} , C_{24} (as appropriate, if <50% C_{24} values are BLOQ) at each dose level will be natural log-transformed and evaluated with a linear mixed effects model containing a fixed effect for treatment and panel, and a random effect for participant. Kenward and Roger's method will be used to calculate the denominator degrees of freedom for the fixed effects. Ninety-five percent confidence intervals for the least squares means for each treatment will be

constructed on the natural log scale and will reference the t-distribution. Exponentiating the least-squares means and lower and upper limits of these confidence intervals will yield estimates for the population geometric means and confidence intervals about the geometric means on the original scale.

Secondary (PBV): Individual PBV will be natural log transformed and analyzed in a linear mixed effects model with fixed effects for dose, time, dose by time interaction and a random effect for subject. The dependent variable is: $\log(\text{PBV at X hour}) - \log(\text{PBV at 0 hour})$. An unstructured covariance matrix for each treatment will be used to allow for unequal variances and different correlations across time and treatment via the REPEATED statement in SAS PROC MIXED (a similar model would be acceptable using R) Kenward and Roger's method will be used to calculate the denominator degrees of freedom for the fixed effects (DDFM=KR). If the model fails to converge, a simpler covariance structure such as compound symmetry may be used. The difference in least squares means on the log scale will be calculated for MK-5475 postdose vs. predose at each time point (1, 3, 8 and 24 hours) at each dose level. These mean differences will be exponentiated to obtain the ratio of geometric means for PBV ($\text{MK_postdose} / \text{MK_predose}$) at each dose level.

Exploratory

The relationship between dose or plasma concentration and pharmacodynamic variables

PVR, pulmonary arterial pressure, cardiac output/cardiac index (CO/CI), systemic vascular resistance, mixed venous oxygen saturation and arterial oxygenation in participants with pulmonary arterial hypertension will be explored graphically. Upon visual inspection, additional model-based analysis might be employed to further explore the pharmacokinetic-pharmacodynamic relationship.

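### 480 µg is added partly to explore exposure against delivered dose, but the PK analysis stops at a geometric mean and interval per dose and plans no slope or between-dose comparison

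*Combined protocol and SAP*

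**What the plan says.** Two sections give a reason for the top dose. Section 4.2 says that 480 µg is given "to further explore the range of possible safe and effective doses of MK-5475". Section 4.3.2 says that it is given "In order to further explore the relationship between systemic exposure and delivered dose at higher doses", and adds that "the resulting systemic exposure is projected to be approximately 3.5nM*hr AUC 0-24h". The same section refers to "the observed direct proportionality between delivered dose and systemically measured PK" without giving an estimate or interval for it.

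For the analysis, section 9.6 (Secondary PK) states that each log-transformed parameter is "evaluated with a linear mixed effects model containing a fixed effect for treatment and panel, and a random effect for participant". Exponentiating the least-squares means and their 95% limits is to "yield estimates for the population geometric means and confidence intervals about the geometric means on the original scale". Sections 9.4 and 9.6 limit this to Panel A Part 1 Periods 1-3 and to Period 1 of Panels B, C and D.

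The only relationship analysis in 9.6 is exploratory. It sets dose or concentration against haemodynamic and oxygenation variables, and its allowance for further modelling covers PK-PD only.

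**The concern.** The dose justification asks how exposure changes with delivered dose. The analysis answers a narrower question: what exposure was at each dose. It contains no log-dose term, dose-normalised parameter, ratio between doses or slope.

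Comparing the per-dose means by eye is a weak substitute. In the PK periods in scope, 120, 165 and 240 µg come from Panel A, 300 µg from Panels B and C, and 480 µg from Panel D. A comparison across 240, 300 and 480 µg therefore mixes differences between people with differences in dose, and section 2.2.3 reports moderate to high variability both between and within PAH participants.

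At stake is how the exposure data are read against the 4.5 nM*hr dog reference. From 120 to 480 µg, a slope of 1.0 means 4-fold exposure and a slope of 1.3 means 4^1.3 = 6.1-fold.

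**Working it through.** **The protocol's projection.** Proportional scaling to 480 µg is AUC × 480/dose.
- From the 300 µg means in 2.2.3 (2.08 to 2.35): 2.08 × 1.6 = 3.33 and 2.35 × 1.6 = 3.76, midpoint 3.54. This reproduces the stated 3.5 nM*hr.
- From Panel A at 240 µg in 4.3.2 ("with AUC 0-24h of 1.42 nM*hr"): 1.42 × 2 = 2.84.
- From the 240 µg range in 2.2.3 (1.04 to 1.71): 2.08 to 3.42.
- From the 360 µg range in 2.2.3 (1.21 to 4.28): 1.61 to 5.71.

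The projection depends on which dose it is scaled from, so proportionality is not settled by the data to date.

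**Implied slope from 240 to 300 µg.** Section 2.2.3 says that the 300 µg "dose level ranged from 2.08 to 2.35 nM*hr across study panels". Slope = ln(AUC300/AUC240) / ln(300/240), with ln(1.25) = 0.223.
- Lowest: ln(2.08/1.71)/0.223 = 0.88.
- Highest: ln(2.35/1.04)/0.223 = 3.65.
- With the single Panel A figure of 1.42: 1.71 to 2.26.

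The full range includes 1, and the two doses were taken by different people.

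**Can the planned model supply a between-dose comparison?** Coding the in-scope periods with an intercept, five doses and four panels gives a design of rank 6. A connected treatment-plus-panel design would need 1 + 4 + 3 = 8. Only the contrasts among 120, 165 and 240 µg are estimable. No contrast of 300 or 480 µg with another dose is.

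**What a power model would give.** Model: ln(PK) = a + b·ln(dose) + participant intercept + error. SE(b) is the square root of the slope element of (X'V⁻¹X)⁻¹. V has within-participant variance on the diagonal plus between-participant variance shared by records of the same person.

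Sample sizes:
- Panel A follows Table 3, with 6 active records per Part 1 dose.
- Table 1 caps Part 2 at 24 and sets a Panel C minimum of 6. If all 8 of Panel A continue, 8 + 4 + 6 leaves 6 for Panel D.
- That gives 4 + 6 = 10 at 300 µg and 6 at 480 µg.

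Section 9.9 gives no variability, so the log-SDs are assumptions.

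| Log-SD between / within | SE(b), in-scope profiles | SE(b), plus Panel D 120 µg |
|---|---|---|
| 0.4 / 0.3 | 0.179 | 0.109 |
| 0.5 / 0.4 | 0.232 | 0.144 |
| 0.6 / 0.6 | 0.318 | 0.213 |

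At ±1.96 SE, the 95% half-width is about 0.35 to 0.62 in scope and 0.21 to 0.42 with the Panel D profile.

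**Remaining between-panel confounding.** Adding a shared panel deviation with log-SD 0.3 (assumed) to V raises the in-scope SE to 0.233-0.387. With the Panel D 120 µg profile it is 0.112-0.219, almost unchanged, because the 480-versus-120 µg contrast is then within participants.

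**Which profiles are comparable (section 1.3).**
- Panel D's imaging-period samples (predose, 15 and 30 min, 1, 2, 3, 4, 8 and 24 h) match the Period 1 schedule except for the 5-minute sample.
- Panels A-C in that period have only predose, 1, 3, 8 and 24 h.
- Catheterization-period sampling ends at 4.5 h, so it cannot give an observed AUC0-24.

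**The case against.** The case for leaving the plan alone has substance. The listed PK objective is only to obtain preliminary PK data, dose proportionality is not an objective at any level, section 9.8 says there are no hypotheses, and 4.3.2 uses the word explore in a narrative that calls systemic exposure less relevant for an inhaled compound. Per-dose means with intervals are a form of exploration. All of this stands, and it is why the point is minor.

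Three stronger readings are tempting and are not supported:
- A reader might infer that 480 µg yields no estimate and no uncertainty. Section 9.6 plans a geometric mean and 95% CI for every dose, including 480 µg, the highest the protocol allows. Whether those means can be estimated with a fixed panel term is a separate question.
- A reader might infer from 1.42 at 240 µg that exposure rises faster than dose, with a slope of 1.7 to 2.3. The 1.04 to 1.71 range in 2.2.3 widens this to 0.88 to 3.65, which does not exclude proportionality.
- A reader might infer that the study can never answer the question. The data are collected, and section 9.2 allows a later change with an explanation in the study report. What is missing is prespecification.

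It is also fair that a power model on the in-scope profiles alone would still compare different people above 240 µg. That part of the objection is met only by adding the Panel D 120 µg profile. Even then, 480 µg always precedes 120 µg in Panel D, so dose and period order coincide there.

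**Conclusion.** The point holds as a minor one. Exploring exposure against delivered dose is one of two stated reasons for 480 µg. The PK analysis plans neither a slope nor a between-dose comparison, and the planned model cannot supply one involving 300 or 480 µg. The means reported so far leave proportionality open. A usable estimate is within reach: a slope SE of roughly 0.11-0.21 with the Panel D 120 µg profile, against 0.18-0.32 without it. Those SEs rest on the assumed log-SDs, on 10 participants at 300 µg and 6 at 480 µg, and on a single slope across the dose range. The textual gap and the rank result do not depend on those assumptions.

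**What to change.** Add to 9.6, Secondary (PK), a descriptive power model of ln(AUC0-24), ln(AUC0-∞) and ln(Cmax) on ln(dose), with a random participant intercept and no fixed panel term.

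- **Primary data for this model:** Panel A Part 1 and Panels B-D Period 1 profiles on MK-5475, plus the Panel D 120 µg imaging-period profile.
- **Sensitivity analysis, AUC only:** add the sparse imaging-period profiles of Panels A-C, which is also where 360 µg enters.
- **Exclude:** AUC0-24 from the catheterization period.
- **Report:** the slope with its 95% CI, where 1 means proportional, with no test or pass/fail criterion. Keep the planned per-dose geometric means.

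The cost is one extra model and a paragraph of SAP text, with no new samples or participants. Some comparison between panels remains, chiefly for 300 µg, and the report should say so.

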4.3.3 Rationale for Dose Interval and Study Design

In this study, Panel A participants were dosed with single doses of 120 µg, 165 µg, and 240 µg in successive dosing periods. In Panels B and C doses up to 360 µg were given. In the initial clinical studies in healthy volunteers with this compound, 120 µg, 165 µg and 240 µg doses were delivered with acceptable safety, tolerability, and pharmacokinetic data. These doses were delivered with the following supportive data: MK-5475, a sGC stimulator, is not considered a compound with a high degree of uncertainty related to the potential risk of harm to participants, according to the publication "Guideline on Strategies to Identify and Mitigate Risks for First-in-Human and Early Clinical Trials with Investigational Medicinal Products" (European Medicine Agency [EMA]) released July 2017. The degree of uncertainty was determined by careful evaluation of the following: mode of action of MK-5475, presence or absence of biomarkers, the nature of the target, the relevance of available animal models and/or findings in non-clinical safety studies, and the study population.

MK-5475 acts via a well-established mechanism (sGC stimulator), for which a marketed agent acts similarly [Riociguat]. Safety assessment toxicity trials and ancillary pharmacology trials with MK-5475 provide no contraindications to the initiation of clinical trials in people with this compound via the inhaled route. No dose-limiting toxicities were observed in 1 month rat and dog toxicity trials, and substantial preclinical safety margins were obtained over initial human doses. As with the previous study, safety will be ensured by the inclusion of extensive safety monitoring in the clinic, and the fact that MK-5475 is not considered a compound with a high potential for risk of harm, which is supported by both preclinical and clinical evidence. There will be frequent, careful assessments of adverse events throughout the postdose period. This recommendation is in keeping with the projected safety profile and the ability of the clinical site to monitor each participant closely. There will be at least a 7-day washout period between doses for any given participant, which is supported by the half-life of MK-5475 observed in humans (approximately 2 hours).

In Part 2 of the study, participants will receive single doses of 240 µg (Panel A) or 300 µg to 360 µg (Panels B and C) in each of two or three successive periods. Single doses will be given in Panel D (480 µg and 120 µg) in three successive periods. For all panels extensive safety monitoring, and with at least a 7-day washout period will occur between doses for any given participant.

4.4 Beginning and End of Study Definition

The overall study begins when the first participant signs the ICF. The overall study ends when the last participant completes the last study-related telephone-call or visit, withdraws from the study, or is lost to follow-up (ie, the participant is unable to be contacted by the investigator).

A study may be paused during review of newly available preclinical/clinical safety, PK, pharmacodynamic, efficacy, or biologic data or other items of interest, prior to a final decision on continuation or termination of the study. It may be necessary to keep the study open for gathering/reviewing of additional supportive data to optimally complete the objective(s) of the study. If necessary, the appropriate amendment(s) to the protocol and/or

appropriate communication(s) will be generated. The overall study end will then not be identified until the Sponsor has made the decision to end the study following this review period. The Competent Authority(ies) and Institutional Review Board(s)/Independent Ethics Committee(s) [IRB(s)/IEC(s)] will be apprised of the maximum duration of the study beyond the last participant out and the justification for keeping the study open. If the decision has been made to end the study following this review period, the study end will be defined as the date of the Sponsor decision and this end of study date supersedes the definitions outlined above

